13.1.4. Key Secondary Efficacy Analyses

The key secondary efficacy endpoints will compare OCA to placebo on the following:

- Time to first occurrence of MELD score ≥ 15

- Time to liver transplant or death (all-cause)
- Change from Baseline in total bilirubin at end of study
- Change from Baseline in ALP at end of study

The key secondary efficacy analyses will compare OCA to placebo in the ITT population with respect to the key secondary efficacy endpoints. Only adjudicated events will be included in time-to-event analyses. The comparison (hypothesis testing) will be conducted as specified in [Section 13.1.10](#) in a sequential closed testing gate-keeping procedure, provided that the primary efficacy endpoint comparison is statistically significant in favor of the OCA treatment group. If the primary comparison is not statistically significant then comparison of the secondary endpoints will be considered as descriptive and exploratory. This procedure controls the study-wise type I error.

The 2 treatment groups will be compared using the same methodology as specified for the primary efficacy analysis ([Section 13.1.3](#)). The same analyses for key secondary efficacy endpoints will be performed for PP population as a sensitivity analysis.

Analyses of change from Baseline to end of study in ALP and total bilirubin will be compared between treatment groups using analysis of covariance (ANCOVA) with change from Baseline as the dependent variable including treatment group and randomization stratification factor as fixed effects and the Baseline values as a covariate. The same analysis will be carried out using percentage change from Baseline as the dependent variable.

Descriptive statistics of the laboratory values will be summarized by treatment group. The results, change from Baseline, and percentage change from Baseline values, as well as estimates of least-square means, standard errors, and 95% CIs, will be presented by treatment group. Estimates of the mean difference between treatment groups, the standard error of the difference, and 95% CI of the difference will be presented.

13.1.5. Additional Secondary Efficacy Analyses

The following time-to-event secondary efficacy analyses will compare OCA versus placebo using the ITT population:

- Time to each component of the primary efficacy endpoint (except MELD score ≥ 15 which is captured above)
- Time to development of varix/varices
- Progression to cirrhosis
- Time to occurrence of HCC
- Time to liver-related death
- Time to liver-related death or liver transplant
- Time to liver-related death, liver transplant, or MELD score ≥ 15

The same analysis methodology as used for the primary efficacy analysis will be used for these secondary efficacy analyses. Similar endpoints, where available, will be analyzed to compare OCA to historical controls as described below in [Section 13.1.8](#).

Analyses of changes in liver biochemistry (GGT, ALT, AST, conjugated bilirubin, albumin, and INR) will be summarized and analyzed using the same methodology as specified in [Section 13.1.4](#) for the key secondary analyses of change in ALP and total bilirubin.

Progression to cirrhosis will be assessed in the subset of subjects considered noncirrhotic at Baseline using available medical history, clinical, and laboratory assessments as well as baseline TE, where available. Specifically, subjects with no clinical, laboratory, or radiological evidence of cirrhosis at baseline and/or a TE liver stiffness of <16.9 kPa ([Corpechot 2012](#)) will be considered noncirrhotic (See [Section 7.5.4](#)). Progression to cirrhosis will be assessed by the development of clinical, laboratory, or radiological evidence of cirrhosis and/or when liver stiffness increases to ≥ 16.9 kPa during the study in which case histological progression to cirrhosis should be confirmed by biopsy unless not medically indicated. Using this definition for progression to cirrhosis, the percentage of noncirrhotic subjects progressing to cirrhosis during the treatment period will be summarized by treatment group and compared using a Cochran-Mantel-Haenszel test stratified by the randomization stratification factor.

For those subjects enrolled in the biopsy substudy (defined in Addendum 2) progression to cirrhosis identified by the above criteria and improvement in fibrosis/cirrhosis will be confirmed by paired biopsy. Analyses for the histological assessment conducted as part of the biopsy substudy are defined in Addendum 2).

Analyses of changes in MELD score, Child-Pugh score, MRS, IgM, CRP, TNF- α , FGF-19, CK-18, C4, and ELF score will be summarized and analyzed using the Wilcoxon Rank Sum Test to compare treatment groups. The median differences and 95% CI of the median differences between treatment groups will be constructed using Hodges-Lehmann estimate. If the median differences between treatments are not symmetrical around the median, the Sign Test may be used.

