11.1.2. Secondary Assessments

The following secondary efficacy assessments will be measured:

- Individual components of the primary endpoint
- Liver-related death
- Progression to cirrhosis as assessed by the presence of clinical, laboratory, or radiological evidence of cirrhosis and/or liver stiffness (Fibroscan® TE), confirmed by biopsy unless not medically indicated.
 - Histological assessment of disease progression or improvement using paired biopsies in a subset of subjects (defined in Addendum 2).
- HCC confirmed by 2 complimentary imaging modalities, unless confirmed by biopsy.
- Liver biochemistry (see [Table 12](#) for list of analytes to be tested)
- Biomarkers, including other markers of hepatic fibrosis and/or inflammation, to be tested will include: IgM, c-reactive protein (CRP), tumor necrosis factor- α (TNF- α), FGF-19, cytokeratin-18 (CK-18) ELF, and Fibroscan (and others as determined during the course of the study).
- Clinical outcomes, including individual component of the primary endpoint (where available), liver transplant, and death will be compared to historical controls.
- PK of OCA and its conjugates.

- Data will be collected to inform quality of life and cost-effectiveness analyses that are relevant to major health care systems around the world. Quality of life will be assessed by questionnaires (PBC-40, EQ-5D-5L, and FIS) administered annually. Resource utilization information will be collected from the Medical and Surgical Treatment Procedures and Office Visit Log or other CRFs such as number, type and duration of hospitalizations, number of outpatient physician visits (subject reported), and use of concomitant medications.
- Endoscopy will be conducted at all study sites where the device is available to assess for the presence of oesophageal varix/varices at baseline. Throughout the study, any endoscopy performed as part of the annual study assessments or standard of care will be collected in the case report form to assess for the development of varix/varices.

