13.1. Efficacy Analysis

13.1.1. Analysis Populations

The following subject populations will be evaluated and used for presentation and analysis of the data:

- The Intent-to-Treat (ITT) Population will include all randomized subjects who receive any amount of investigational product (OCA or placebo). The ITT Population will be the primary population used for efficacy analyses. Treatment assignment will be based on the randomized treatment.
- The Per Protocol (PP) Population will include all ITT subjects who do not have any major protocol violations that potentially affect the efficacy conclusion. Treatment assignment will be based on the randomized treatment.
- The Safety Population will include all subjects who received any amount of investigational product (placebo or OCA). The Safety Population will be the primary population used for safety analyses. Treatment assignment will be based on the treatment actually received.
- The PK Population will include all OCA subjects who have at least one confirmed fasted analyzable sample. Subjects must have been fasting for approximately 8 hours prior to the visit and must not have any major protocol deviations that potentially affect exposure levels. The PK population will be used for OCA PK analyses.
- The Overall Historical Control Population will include subjects from the United Kingdom (UK) -PBC Group and Global PBC Study Group databases with demonstrated comparability to randomized subjects in this clinical study (747-302) with respect to both subject characteristics and disease progression.
- The UK-PBC Historical Control Population will include subjects from the UK-PBC Group databases with demonstrated comparability to randomized subjects in this clinical study (747-302) with respect to both subject characteristics and disease progression.

- The Global PBC Historical Control Population will include subjects from the Global PBC Study Group database with demonstrated comparability to randomized subjects in this clinical study (747-302) with respect to both subject characteristics and disease progression.

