13.1.9.1. Time to Event Endpoints

For the time to event analyses, subjects who do not experience an event will be censored at the time of their last contact. Subjects with no data after randomization will be considered to have an event on Day 1 (first day of investigational product dosing).

For analyses of the percentage of subjects with an event, subjects with no data after randomization will be considered to have an event.

All time to event endpoints include only adjudicated events. Sensitivity analyses may consider all events regardless of adjudication. Events with discrepant adjudication will be analyzed using both results.

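### Time to development of varices: an unrestricted ITT risk set with censoring at last contact counts unassessed follow-up as varices-free and understates absolute incidence

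*Protocol*

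**What the plan says.** - **Population.** Section 13.1.5 introduces its list with "The following time-to-event secondary efficacy analyses will compare OCA versus placebo using the ITT population", and "Time to development of varix/varices" is one of the items. Section 13.1.1 defines the population: "The Intent-to-Treat (ITT) Population will include all randomized subjects who receive any amount of investigational product". Neither place sets a condition on varices or endoscopy.
- **Method.** Section 13.1.5: "The same analysis methodology as used for the primary efficacy analysis will be used for these secondary efficacy analyses". That means the stratified log rank test, Kaplan-Meier estimates and a stratified Cox model.
- **Censoring.** Section 13.1.9.1: "For the time to event analyses, subjects who do not experience an event will be censored at the time of their last contact". It adds: "Subjects with no data after randomization will be considered to have an event on Day 1".
- **Endoscopy.** Section 11.1.2: "Endoscopy will be conducted at all study sites where the device is available". Section 9.7.4 accepts a baseline endoscopy up to 12 months old. It asks for later ones annually or according to standard of care and the investigator's judgment, and also when platelets fall below 150 x 10^9/L. Table 2 schedules endoscopy at the yearly visit but not at EOT/EOS, and the EOT/EOS procedures in Section 9.7.15 do not list it.
- **Follow-up without visits.** Section 7.9 and Table 8 allow subjects off investigational product to continue by semi-annual telephone contact or by record review only.
- **Varices at entry.** Section 7.5.4.1 lists varices as a cirrhosis indicator at Screening. Among cirrhosis complications, Section 8.3 excludes variceal bleed (present, or within the past 12 months). It does not exclude varices as such.

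**The concern.** A time-to-event analysis needs a risk set of subjects who can still have the event, and follow-up during which the event could have been seen. The stated rules secure neither for varices. A subject at a site without the device may never be examined, yet stays in the denominator as event-free to last contact. A subject whose last endoscopy was in year 2 and who was then followed by telephone contributes all later years as varices-free. A subject with known varices at entry cannot newly develop them but is still counted as at risk.

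Section 13.1.5 handles the neighbouring endpoint differently: progression to cirrhosis is assessed only in subjects who are noncirrhotic at Baseline. Varices have no matching restriction. At stake are the Kaplan-Meier incidence curves and the absolute difference between arms.

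**Working it through.** The protocol states no figure for this endpoint, so there is none to reproduce. The sample-size figures in Section 13.1.2 (127 events, 428 subjects) concern the primary endpoint and are unaffected. The protocol gives no prevalence of varices at entry, no endoscopy coverage and no incidence of varices. **All such shares below are assumptions.** The hazard ratio of 0.60 is borrowed from Section 13.1.2 for illustration.

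**1. Subjects never scoped.** Let I be the true cumulative incidence and u the share never scoped, at equal risk. Reported incidence = I x (1 - u).
- Assume placebo I = 25% at 8 years. With HR 0.60, OCA I = 1 - 0.75^0.6 = 15.9%. The true difference is 9.1 points.

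| u | Placebo reported | Difference reported |
|---|---|---|
| 20% | 25% x 0.8 = 20% | 9.1 x 0.8 = 7.3 points |
| 40% | 25% x 0.6 = 15% | 9.1 x 0.6 = 5.5 points |

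**2. Time after the last endoscopy.** The same reasoning applies to person-time. Under a constant hazard, if a fraction f of the counted time is unassessed, the estimated rate is the true rate x (1 - f).

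**3. Varices at entry, if development means new onset.** Reported incidence = I x (1 - b) x (1 - u), where b is the share with baseline varices and u is the share of the rest never scoped. Take I = 30% and 428 subjects.

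| b | u = 0: reported (truly at risk) | u = 30%: reported (at risk and scoped) |
|---|---|---|
| 10% | 27% (385) | 18.9% (270) |
| 20% | 24% (342) | 16.8% (240) |
| 30% | 21% (300) | 14.7% (210) |

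**4. Hazard ratio with equal shares in both arms.** Let q be the share not truly at risk. Survival is then q + (1 - q) x 0.70 on placebo and q + (1 - q) x 0.70^0.6 on OCA at 8 years. Solving the Cox score equation over 8 years with exponential onset among those at risk and a true HR of 0.60 gives:
- q = 10%: 0.605
- q = 30%: 0.614
- q = 50%: 0.623

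Hand check at q = 50%: ln(0.5 + 0.5 x 0.807) / ln(0.5 + 0.5 x 0.70) = (-0.1013) / (-0.1625) = 0.623.

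**5. Varices at entry, if they were counted as events.** Reported incidence becomes b + (1 - b) x I. With placebo I = 25%, this is 32.5% at b = 10% and 40% at b = 20%, an overstatement.

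**The case against.** **The protocol does not bar a restriction.** The ITT header in Section 13.1.5 also covers progression to cirrhosis, which the same section then limits to a baseline subset. The header can therefore be read as a base population. Section 11.1.2 separates presence of varices at baseline from their later development, which points to new onset. A SAP, not available here, may supply an at-risk subset. This is fair as to the header. But no such limit is stated for varices, and the last-contact rule is stated outright for time-to-event analyses. Followed as written, the text gives unassessed time as event-free time.

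**The Day 1 rule does not rescue it.** That rule covers subjects with no data at all after randomization, not those who were followed but never scoped.

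**The size is uncertain.** Section 9.7.4 directs endoscopy partly at subjects with low platelets, and Section 11.1.2 collects standard-of-care endoscopies. If never-scoped subjects have lower risk, the understatement is smaller than in step 1. This stands.

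**A reader might infer serious dilution of the hazard ratio.** Adding 10-20% prevalent cases to both arms as events would move a true 0.60 to about 0.71-0.77. That requires prevalent varices to count as events, which would overstate incidence, and it goes against the distinction drawn in Section 11.1.2. Sites with the device also scope at Day 0 or accept a recent report, so most subjects scoped later should have a baseline result. The documents do not support that range.

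**A reader might also infer bias between arms.** Section 5.5.2.3 anticipates possible differences between arms in ancillary treatments and diagnostics, but nothing in the protocol shows unequal endoscopy coverage.

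**Conclusion.** The point holds as a minor one. Under Sections 13.1.5 and 13.1.9.1 as written, subjects never scoped, and time after the last endoscopy, count as varices-free without assessment. This understates absolute incidence and the absolute difference. The amount cannot be fixed from the protocol: with 20-40% unscoped at equal risk, a true 25% reads as 20-15% and a true 9.1-point difference as 7.3-5.5 points.

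An unconditional statement that varices at entry understate incidence would go too far. They do so if development means new onset, and they do the opposite if prevalent varices are counted; the term is not defined. With balanced arms the comparison is barely affected (0.605-0.623 for a true 0.60). Section 13.1.10 places this endpoint outside the testing hierarchy, for descriptive and exploratory purposes. The primary result, alpha, power and sample size are untouched.

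**What to change.** Add to Section 13.1.5, for this endpoint only:

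- The analysis set is ITT subjects with a baseline endoscopy free of varices. This is a pre-treatment criterion, so the comparison remains between randomized groups.
- Development means new onset on an endoscopy after that baseline examination.
- Subjects without an event are censored at their last varices-free endoscopy, as an exception to the last-contact rule in Section 13.1.9.1.
- As sensitivity analyses, add by delayed entry the subjects without a baseline endoscopy whose first on-study endoscopy is varices-free, and treat onset as interval-censored between endoscopies.

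This is a wording change that uses data already collected. The cost is a smaller denominator for a descriptive secondary endpoint. Not all of those left out are uninformative: subjects with no baseline endoscopy but a clear later one carry information from that point, and the delayed-entry analysis recovers it.

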Progression to cirrhosis will be assessed in the subset of subjects considered noncirrhotic at Baseline using available medical history, clinical, and laboratory assessments as well as Baseline TE where available. Specifically, subjects with no clinical, laboratory, or radiological evidence of cirrhosis at Baseline and/or a TE liver stiffness of < 16.9 kPa (Corpechot 2012) will be considered noncirrhotic. Progression to cirrhosis will be assessed by the development of clinical, laboratory, or radiological evidence of cirrhosis and/or when liver stiffness increases to ≥ 16.9 kPa during the study in which case histological progression to cirrhosis should be confirmed by biopsy unless not medically indicated. Using this definition for progression to cirrhosis, the percentage of noncirrhotic subjects progressing to cirrhosis during the treatment period will be summarized by treatment group and compared using a Cochran–Mantel–Haenszel test stratified by the randomization stratification factor.

For those subjects enrolled in the biopsy substudy (defined in Addendum 2) progression to cirrhosis identified by the above criteria and improvement in fibrosis/cirrhosis will be confirmed by paired biopsy. Analyses for the histological assessment conducted as part of the biopsy substudy are defined in Addendum 2.

Further details on efficacy, health outcomes, and PK analyses are specified in [Section 13](#).

Safety Analyses

Safety data, including AEs, AEs of special interest including pruritus and hepatic safety, vitals, electrocardiogram, and clinical laboratory results will be summarized by treatment group for the Safety Population.

Sample Size Justification

The target population is subjects who are at higher risk of liver-related clinical complications. Eligible subjects will have a diagnosis of PBC with bilirubin levels $>ULN$ and $\leq 5x ULN$ and/or $ALP >3x ULN$. The following assumptions were used in sample size calculations:

- Exponential survival curves, placebo survival estimate of 0.6 at 8 years with a hazard ratio of 0.60, and total study duration of 10 years (from first subject enrolled), allowing for 4 years of subject accrual and 6 years of follow-up
- Subjects will be randomized in a 1:1 ratio to placebo or OCA.
- The 2 groups will be compared using a 2-sided log rank test at the 5% level of significance.

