7.5.4. Assessing Cirrhosis

7.5.4.1. Determination for Dosing Regimen

To determine which dosing regimen subjects should follow, the presence or absence of cirrhosis should be assessed by the Investigator at Screening Visit 1. Acceptable methods of confirming (via medical history) or assessing cirrhosis for purposes of determining dosing is defined as a

subject who has documented evidence or presence of one or more of the following cirrhosis indicators:

Biopsy results consistent with PBC Stage 4 ([Ludwig 1978](#))

- TE Median Value ≥ 16.9 kPa ([Corpechot 2012](#))
- The presence of any of the following (unless exclusionary per [Section 8.3](#)) in the absence of acute liver failure:
 - Varices
 - Ascites
 - Radiological evidence of cirrhosis (nodular liver or enlargement of portal vein and splenomegaly)
- Combined low platelet count ($<140\,000/\text{mm}^3$) with:
 - persistent decrease in serum albumin, or
 - elevation in prothrombin time /INR (not due to antithrombotic agent use), or
 - elevated bilirubin ($2\times$ ULN)

Subjects who exhibit no evidence of cirrhosis by the above methods of assessment will be dosed using the Standard Dosing Regimen, while those who do exhibit evidence of cirrhosis by one or more of the above methods will be dosed using the Modified Dosing Regimen according to their Child-Pugh Score calculated in the electronic case report form (eCRF) (see [Appendix A](#) and [Section 7.3](#)).

Cirrhosis status should be reassessed as clinically indicated throughout the study. Any change in cirrhosis status will necessitate re-evaluation of the dosing regimen.

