7.5.4.2. Progression to Cirrhosis

When a subject identified as noncirrhotic at Baseline per the criteria listed in [Section 7.5.4](#) exhibits any signs or symptoms associated with progression to cirrhosis, as defined by the same criteria, the subject should also be assessed by Fibroscan® TE where available and progression to cirrhosis confirmed by biopsy (centrally read) unless not medically indicated. Laboratory samples needed to obtain noninvasive scores of liver fibrosis (ELF, and aspartate aminotransferase to platelet ratio index [APRI]) will also be collected when a subject develops evidence of progression to cirrhosis.

Full instructions concerning the sample collection methods, processing, labeling, and shipping will be provided by the Sponsor in a study-specific histology manual. Collection supplies will be provided by the central laboratory.

Sites participating in the paired biopsy substudy must confirm progression to cirrhosis by biopsy as per the information outlined in protocol Addendum 2.

All suspected cases of progression to cirrhosis should be submitted for adjudication regardless of the availability of transient elastography or biopsy results.

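### The noncirrhotic at-risk set is defined with an and/or that contradicts Section 7.5.4, and progression to cirrhosis is given two analyses without saying which governs

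*Protocol*

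**What the plan says.** **At-risk set.** Section 13.1.5 restricts progression to cirrhosis to subjects noncirrhotic at baseline. It defines these as "subjects with no clinical, laboratory, or radiological evidence of cirrhosis at baseline and/or a TE liver stiffness of" <16.9 kPa, followed by a cross-reference to Section 7.5.4. The Synopsis repeats the rule without the cross-reference: "subjects with no clinical, laboratory, or radiological evidence of cirrhosis at Baseline and/or a TE liver stiffness of" <16.9 kPa.

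**Cirrhosis elsewhere.** Section 7.5.4.1 calls cirrhotic any subject "who has documented evidence or presence of one or more of the following cirrhosis indicators": biopsy stage 4; TE of 16.9 kPa or more; varices, ascites or radiological evidence; or low platelets with a further laboratory abnormality. Section 7.5.4.2 uses the same criteria for baseline status: "When a subject identified as noncirrhotic at Baseline per the criteria listed in" Section 7.5.4.

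**Event.** "Progression to cirrhosis will be assessed by the development of clinical, laboratory, or radiological evidence of cirrhosis and/or when liver stiffness increases to" 16.9 kPa or more during the study, with biopsy confirmation unless not medically indicated.

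**Analysis.** Section 13.1.5 lists progression to cirrhosis among ITT time-to-event analyses and states: "The same analysis methodology as used for the primary efficacy analysis will be used for these secondary efficacy analyses". That method is the stratified log-rank test, Kaplan-Meier estimates and stratified Cox model of Section 13.1.3. Later the section says "the percentage of noncirrhotic subjects progressing to cirrhosis during the treatment period will be summarized by treatment group" and compared by a stratified CMH test.

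**The concern.** If one indicator makes a subject cirrhotic, noncirrhotic must mean that none is present. With *and/or*, a subject with TE of 12 kPa and varices qualifies as noncirrhotic, and so does one with TE of 20 kPa and no other sign. Such subjects can be in the trial: Section 8.3 excludes cirrhosis only when complicated, and Section 7.3 doses Child-Pugh A, B and C subjects. They are not at risk of becoming cirrhotic, and including them can dilute a real difference.

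The two analyses differ in test and follow-up window, and possibly in events: Section 13.1.9.1 limits time-to-event endpoints to adjudicated events, while the CMH sentence refers only to the definition just given. Without a stated priority, the choice could be made after seeing both results.

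The window matters because stopping study drug is expected. A switch to commercial OCA ends it (Section 9.2.1), Section 5.5.2.3 names commercial OCA as a potential source of bias, and hepatic deterioration triggers interruption or discontinuation (Tables 4, 5 and 7). Subjects who stop are expected to stay in follow-up (Sections 7.9 and 13.1.9), so an on-drug window would discard data that the protocol works to collect.

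**Working it through.** The protocol gives no figure for this endpoint. The 127 events and 428 subjects of Section 13.1.2 belong to the primary endpoint and do not depend on it.

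**1. The definitions side by side**

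| Baseline status | 7.5.4.1 | 13.1.5, read literally |
|---|---|---|
| No indicator, TE <16.9 | noncirrhotic | noncirrhotic |
| Varices, TE <16.9 | cirrhotic | noncirrhotic |
| No other sign, TE ≥16.9 | cirrhotic | noncirrhotic |
| Varices, TE ≥16.9 | cirrhotic | cirrhotic |

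The middle rows conflict. Section 13.1.5 also does not name the biopsy criterion.

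**2. Dilution**

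Assumed: true progression of 24% on placebo, and a hazard ratio of 0.60 borrowed from the primary design, which gives 1 − 0.76^0.6 = 15.2% on OCA (risk ratio 0.633). Let p be the share of the set already cirrhotic.

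- *Upper bound: every such subject counts as an event.* Observed percentage = (1 − p) × true + p.
  - p = 5%: 27.8% v 19.4%, ratio 0.70
  - p = 10%: 31.6% v 23.7%, ratio 0.75
  - p = 20%: 39.2% v 32.2%, ratio 0.82
- *Other extreme: none ever counts.* At p = 10%: 0.9 × 24% = 21.6% v 0.9 × 15.2% = 13.7%. The ratio stays at 0.633 and the difference shrinks from 8.8 to 7.9 points.

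A simulation under the upper-bound reading (4,000 trials per setting, unstratified, 300 subjects, placebo hazard 0.05 per year, hazard ratio 0.60, stopping 0.05 per year in both arms, prevalent cases counted at Month 3) gives this power:

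| p | CMH | Log-rank |
|---|---|---|
| 0% | 51% | 54% |
| 5% | 43% | 44% |
| 10% | 37% | 36% |
| 20% | 29% | 26% |

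The log-rank test does not repair a faulty at-risk set.

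**3. On-drug percentage with no drug effect**

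From Section 13.1.2: accrual over 4 years and a 10-year study, so potential follow-up is uniform on 6 to 10 years. Assumed: progression hazard h, the same in both arms, and stopping rate d, independent of progression. The expected percentage progressing before stopping is

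P = h/(h+d) × {1 − [e^(−6(h+d)) − e^(−10(h+d))] / [4(h+d)]}.

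With h = 0.05 per year:

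- d = 0.10: 0.333 × [1 − (0.4066 − 0.2231)/0.6] = 23.1%
- d = 0.20: 0.200 × [1 − (0.2231 − 0.0821)/1.0] = 17.2%

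With h = 0.03 the same pair gives 14.8% and 10.9%.

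Simulated rejection rates at the two-sided 5% level (200 or 300 subjects, h of 0.03 or 0.05):

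| Stopping per year, arm v arm | Percentage test |
|---|---|
| 0.10 v 0.10 | 4.5–5.0% |
| 0.10 v 0.15 | 7–11% |
| 0.05 v 0.10 | 8–15% |
| 0.10 v 0.20 | 13–25% |

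The log-rank test, censoring at stopping, stays at 4.6–5.8% throughout. The first row includes staggered entry and holds its level, so staggered entry alone does no harm.

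**The case against.** The strongest reply is that this is loose wording with the remedy nearby. Section 13.1.5 cross-refers to Section 7.5.4, and the preceding sentence says that TE is used where available, so *and/or* may only be meant to cover missing TE. That is a plausible intent, but the sentence that states the rule still says something else, and the Synopsis lacks the cross-reference.

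A reader might infer that wrongly admitted subjects progress automatically at their first assessment. The text does not support that. The event requires evidence to develop, or stiffness to rise to the threshold during the study, with biopsy confirmation where indicated; suspected cases go to adjudication. The upper-bound figures are therefore not a forecast. A subject with TE of 20 kPa at baseline who later develops varices could still be counted as progressing to a state that Section 7.5.4.1 had already assigned.

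A reader might also infer that progression is compared only as a crude on-treatment percentage. It is not: the same section specifies the time-to-event analysis, which handles unequal follow-up. Nor are a percentage and a time-to-event analysis incompatible; Section 13.1.9.1 foresees both. What is missing is priority.

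Finally, *treatment period* is not defined, and the Synopsis entry on duration of treatment describes the whole event-driven study. Reading it as time on study drug is one possibility. The bias in step 3 is conditional on that reading and on stopping rates that differ by arm.

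**Conclusion.** The point holds as a contradiction to reconcile and an unranked pair of analyses. The at-risk rule in Section 13.1.5 and the Synopsis conflicts with Sections 7.5.4.1 and 7.5.4.2, and subjects already cirrhotic by those criteria could enter the set. The percentage comparison is vulnerable if its window is time on drug and discontinuation differs by arm; the documents give neither the size nor the direction of such a difference.

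The figures above show direction and plausible range only. Subset size, progression rate, share of prevalent cases and stopping rates are all assumed, and stopping was taken as independent of progression.

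The consequence is limited. Progression to cirrhosis is a stated secondary objective (Section 6.2), but it lies outside the gatekeeping hierarchy, and Section 13.1.10 makes tests on such endpoints descriptive and exploratory. The primary analysis, sample size and type I error control are unaffected.

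**What to change.** In Section 13.1.5 and the Synopsis, define noncirrhotic at baseline, for this analysis, as meeting none of the Section 7.5.4.1 indicators, including TE <16.9 kPa where TE was measured. Subjects without a TE value are classified on the remaining indicators. The change concerns the analysis set only and leaves the dosing determination untouched.

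State that the treatment comparison is the stratified log-rank test and Cox model already named in the section, applied to time from randomization to adjudicated progression over all follow-up, on and off treatment. Keep the percentage progressing as a descriptive summary without a test, and define its window.

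The cost is wording in two places and a somewhat smaller at-risk set. No new data collection is needed.
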